7.2 Exclusion criteria

For the Screening Log & Registry

None

For the Randomised Trial

- 1. eGFR <30ml/minute/1.73m² (if clinically appropriate, the dose of other agents such as loop diuretics, ACE inhibitors, angiotensin receptor blockers, beta-blockers and sacubitril-valsartan may be adjusted to allow eGFR to increase)
- 2. Systolic BP <90mmHg
- 3. Uncorrected valve disease as the main cause of heart failure in the investigators opinion

Version 5.0 22 July 2021 Page 26 of 82

- 4. Hepatic encephalopathy or known severe liver disease
- 5. Infection currently requiring intravenous antibiotics or temperature >38oC
- 6. Myocardial ischaemia currently requiring intravenous therapy or coronary intervention in the previous 7 days
- 7. Arrhythmia requiring urgent cardioversion or intravenous therapy
- 8. Severe hyperkalaemia requiring, in the investigator's opinion, intravenous treatment or a potassium-binding agent
- 9. The patient is already receiving a potassium-binding agent (this includes patiromer) or the treating physician has already decided to use one
- 10. Known hypersensitivity to patiromer or any of the excipients
- 11. Known intolerance to both spironolactone and eplerenone (not including hyperkalaemia)
- 12. Known hypersensitivity to the active substance or excipients of spironolactone and eplerenone as per the current Summary of Product Characteristics (Note: actual medicine supplied to participants will vary depending on local arrangements)
- 13. Women of childbearing potential. For the purposes of this trial this means any woman aged <60 years unless they have had a hysterectomy or bilateral tubal ligation or are aged >50 years and have undergone the menopause and had amenorrhea for at least 3 years
- 14. Patients taking the following systemic medicines:
 - strong inhibitors of CYP 3A4 (e.g. itraconazole, ketoconazole, ritonavir, nelfinavir, clarithromycin, telithromycin and nefazodone)
 - Lithium
 - Tacrolimus or Cyclosporin
- 15. The combination of an angiotensin converting enzyme (ACE) inhibitor and an angiotensin receptor blocker (ARB)
- 16. Rare hereditary problems of galactose or fructose intolerance, Lapp lactase deficiency or glucosegalactose malabsorption
- 17. Known amyloid heart disease
- 18. Cancer likely to cause death or major disability within the next three years
- 19. Patients requiring mechanical circulatory support, and
- 20. Patients who do not develop a serum potassium >5.0mmol/L despite receiving up to 100mg/day of spironolactone or 50mg/day of eplerenone during the run in phase.

Potentially suitable patients may be considered for the randomised controlled trial as soon as arrhythmia, infection, renal dysfunction, hypotension etc. have been corrected to the satisfaction of the investigator and the above noted exclusion criteria no longer exist.

Serum magnesium will be measured during the trial and magnesium supplements given if serum magnesium drops below 0.75mmol/L (1.5mEq/L or 1.8mg/dL). Accordingly, hypo-magnesaemia is not an exclusion criterion for participation. Potassium sparing diuretics (amiloride or triamterene) other than MRA and potassium supplements should be withdrawn unless the patient is hypokalaemic and as soon as hypokalaemia resolves to allow higher doses of MRA to be used.

Co-enrolment in observational studies of routine clinical practice is permitted. Sponsors and CIs must be contacted to discuss in advance.

Co-enrolment in interventional observational studies or randomised trials requires agreement between the Chief Investigators, Trial Steering Committees and Sponsors for the respective studies/trials. The following issues will be taken into account when making this decision:

- Participant burden: does participation in both studies increase the number of participant visits, pill-burden or other activity and if so, by how much?
- Potential interactions between investigational medicinal products that might affect participant safety
- Study design: co-enrolment into double-blind trials should generally be avoided
- Endpoints: could participation in both studies influence the outcome of either study?

8. TRIAL PROCEDURES

Patients with worsening heart failure, either in hospital or in the community, will be identified. Limited information (as advised by the HRA) will be retained in a screening log for those who do not consent or who are not approached for the registry. Patients who consent to participate in the registry will have personal identifiers and further medical information collected and will be followed-up, long-term, through linkage to their electronic medical records. Registry participants will be asked to take part in the randomised trial if they fulfil all of the eligibility criteria. Consenting patients who have a serum potassium >5.0mmol/L will be randomised (after an 8.4g test-dose of patiromer to ensure participant acceptance; note - there is no requirement for the participant to consume the full dose and failure to do so will not constitute a protocol deviation) either to patiromer or not (open-label). If serum potassium is <5.0mmol/L, MRA will be initiated or increased to target doses for a "run-in" period of up to 35 days. If serum potassium increases to >5.0mmol/L, the participant may be randomised. Those who do not develop hyperkalaemia despite receiving the run-in target dose of MRA within 35 days of enrolment are not eligible for randomisation and will return to standard care.

Version 5.0 22 July 2021 Page 28 of 82

8.1 **Schedules of Procedures**

8.1.1 Schedule of Procedures for Screening Log (-00), the Registry (-0) and Randomised Trial (up to 60 days)

		Mostly in hospital / day-care								Majority of care at follow-up in clinic T4 T5 T6		
Visit	-00									T5	T6	
Days				-X	1	3	5	7*	14	30	60	
Window +/- days			NA	35	1	1	2	3	5	10	14	
Consent		Χ	Χ									
History	Χ	Х										
Frailty Scale	Χ	(X)										
Symptoms/NYHA		X			X	X	X	Χ	Х	Χ	Χ	
PGA						Х	Х	X	Χ	Х	Х	
CV Therapy	Χ	Χ			X	Х	Х	Χ	Х	Х	Х	
Non-CV Med♦		Χ			Χ			Х			Х	
Height	Х	Χ			Х			Х			Х	
Weight	Х	Χ		Χ	Х	Х	Х	Х	Х	Х	Х	
Vital Signs	Х	Χ*		Χ	X*	Х	Х	X*	Х	Х	X*	
Physical Exam		Χ			Х			Х			Х	
Oedema Grade		Χ			Х	Х	Х	Х	Х	Х	Х	
Orthopnoea Test		Χ			Х			Х			Х	
ECG trace		Χ										
Electronic ECG		Opt			Х			Х			Х	
Echocardiogram	Х	Opt									Opt	
Haematology		Χ			Χ			Χ			X	
Biochem Safety	Χ			Χ		X	X		Х	Χ		
Biochem+		Χ			X			Χ			X	
Spot Urine		Χ			Х			Х			Х	
Biomarkers		Opt			Х			Х			Х	
KCCQ/EQ5D		Opt			Х			Х			Х	
Walk Test @		Opt			Χ			Х			Χ	
Titration/Compliance						Х	Х	Х	Х	Х	Х	
AE					Х	Х	Х	Х	Х	Х	Х	
SAE				Х	Х	Х	Х	Х	Х	Х	Х	
Dispensing				Χ	Х			Х			Х	

^{-00 =} screening log; -0 = consented registry; 0 = consent for trial; RI = run-in phase awaiting rise in potassium. κ = randomisation. T = titration visit. Day 7* = day 7 or discharge if sooner. EOS = end of trial. CV = cardiovascular. X* vital signs measured during orthopnoea (orthop) test. Opt = optional

Local Haematology = Haemoglobin, Haematocrit, White Cell Count, Neutrophils, Lymphocytes.

Local Biochemistry = Sodium, Potassium, Urea, Creatinine.

Local Biochemistry+ = Sodium, Potassium, Magnesium, Bicarbonate, Calcium, Phosphate, Urea, Creatinine, Bilirubin, Transaminases, Alkaline Phosphate, Albumin.

KCCQ = Kansas City Cardiomyopathy Questionnaire. EQ5D = EuroQol 5-dimension questionnaire. NYHA = New York Heart Association functional class. PGA = patient global assessment on a 7-point scale ranging from much worse to much better.

[@] for patients who feel unable to do these tests, the reason will be recorded. AE / SAE = adverse / serious adverse events.

[♦] includes vaccine history

8.1.2 Schedule of Procedures for the Randomised Trial (long-term follow-up)

		Majority of care at follow-up in clinic									
Visit	T7	T8	T9	T10	T11	T12	T13	T14	TX	EOS	
Months	3	6	9	12	15	18	21	24	+3		
Window +/- days	14	14	14	14	14	14	14	14	14	NA	
Consent											
History											
Symptoms/NYHA	Х	Х	Х	Х	Х	Х	Х	Х	Х	Х	
PGA	Х	Х	Х	Х	Х	Х	Х	Х	Х	Х	
CV Therapy	Х	Х	Х	Х	Х	Х	Х	Х	Х	Х	
Non-CV Med		Х		Х				Х			
Height											
Weight	Х	Х	Х	Х	Х	Х	Х	Х	Х	Х	
Vital Signs	Х	X*	Х	Χ*	Х	Х	Х	Χ*	Х	Х	
Physical Exam											
Oedema Grade	Χ	X	X	X	X	X	X	X	Х	X	
Orthopnoea Test		X		X				X			
ECG trace											
Electronic ECG		X		X				X			
Echocardiogram		Opt		Opt				Opt			
Haematology		X		X				X			
Biochem Safety	Χ		X		Χ	X	Χ		X	X	
Biochem+		Х		X				X			
Spot Urine		X		Х				Х			
Biomarkers		Х		Х				Х			
KCCQ/EQ5D		Х		Х				Х			
Walk Test @		Х		Х				Х			
Titration/Compliance	Χ	Х	X	X	Χ	Χ	Χ	X	X	X	
AE/ SAE	Х	Х	Х	Х	Х	Х	Х	Х	X	X	
Dispensing	Χ	X	X	X	Χ	Х	Χ	X	Х		

T = titration visit. TX = repeat visits every 3 months for dispensing and titration. EOS = end of trial. CV = cardiovascular. X* vital signs measured during orthopnoea (orthop) test. Opt = optional

KCCQ = Kansas City Cardiomyopathy Questionnaire. EQ5D = EuroQol 5-dimension questionnaire. NYHA = New York Heart Association functional class. PGA = patient global assessment on a 7-point scale ranging from much worse to much better.

@ for patients who feel unable to do these tests, the reason will be recorded. AE / SAE = adverse / serious adverse events.

Key visits for the assessment of clinical efficacy and endpoints are

- Day 7 (+/-3 days or discharge from hospital or day-care)
- Day 60 (+/-14 days)
- And at 6 months (+/-14 days) months,12 months (+/- one month) and 24 months (+/- one month)

Additional visits are required to assess symptoms and safety (serum potassium/magnesium, renal function, blood pressure). Patients may be evaluated in the community or clinic setting as convenient but will have to attend hospital visits to obtain trial IMP (patiromer, spironolactone/eplerenone).

In addition, if doses of patiromer or MRA are changed, blood pressure and serum electrolytes and creatinine should be re-checked both after 7-12 days and after 30-45 days. If the patient becomes acutely unwell for any reason, blood pressure, serum electrolytes and creatinine should be re-checked. Serum potassium should also be checked within 48 hours of stopping patiromer.

Version 5.0 22 July 2021 Page 30 of 82

Local Haematology = Haemoglobin, Haematocrit, White Cell Count, Neutrophils, Lymphocytes.

Local Biochemistry = Sodium, Potassium, Urea, Creatinine.

Local Biochemistry+ = Sodium, Potassium, Magnesium, Bicarbonate, Calcium, Phosphate, Urea, Creatinine, Bilirubin, Transaminases, Alkaline Phosphate, Albumin.

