3. ASSESSMENT AND MANAGEMENT OF RISK

The independent data monitoring committee (IDMC) will review all serious adverse events with particular attention to interventions for and serious consequences of hypo- and hyperkalaemia, symptomatic hypotension and renal dysfunction and may recommend changes to the protocol during the course of the trial.

Patiromer binds potassium in the gut and is not absorbed. It has no direct cardiovascular action. The initial dose is 8.4g/day suspended in water or apple juice and it may be increased to 16.8g or 25.2g/day, either by taking multiple sachets or a higher-dose sachet. Patiromer suspension has a slightly gritty texture that some patients may be unwilling to take regularly. A test dose will be given prior to randomisation to ensure that the patient understands how to prepare patiromer and is willing to take patiromer long-term. Due to the potential for patiromer to bind to co-administered oral medicines in the gastrointestinal tract, administration of patiromer should be separated by at least 3 hours from other oral medicinal products. However, at investigator-discretion, patiromer may be co-administered with other medicines if data are available to indicate bioavailability is unlikely to be affected, based on

Version 5.0 22 July 2021 Page 18 of 82

in vivo (in healthy volunteers) and in vitro studies (22, 23). A list of medicines that may be coadministered with patiromer is provided in section 9.8.

Patiromer may cause constipation in some people. This may be managed by diet, treatments for constipation or by reducing the dose of patiromer.

Patiromer may cause hypokalaemia and hypomagnesaemia (defined in this protocol as serum magnesium <0.75mmol/L) if insufficient doses of MRA are given (this may apply to participants in either arm of this trial). If the dose of MRA cannot be increased due to hypotension or renal dysfunction, this may be corrected by magnesium supplements or by reducing the dose of patiromer.

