An important risk is the discontinuation of one agent (either patiromer or MRA) but not the other. Participants will be educated accordingly by investigators and provided educational material, and reminders on the labelling of the relevant IMP. Participants will also be provided with a trial safety-card which they will be asked to carry with them at all times and show the card to any doctors or healthcare professionals who are involved in their care. Investigators will be educated by the protocol, site initiation visits, webinars and regular teleconferences. Participants' primary care physicians will be sent information by letter. Patients will receive supplies of both patiromer and MRA as appropriately labelled trial medications. They should be taken approximately three hours apart as indicated in patiromer's license. Treatment will be open-label, which will reduce confusion and uncertainty and avoid the needs and complexity of emergency un-blinding.

Patients will be closely monitored in this trial, with regular measurements of potassium, magnesium, renal function and blood pressure.

Women with childbearing potential will be excluded as the risks of patiromer in pregnancy are unknown (although unlikely to be a problem) and spironolactone poses risks to the developing foetus. Moreover, few women of childbearing potential are likely to be eligible for this trial. Most patients will be aged >60 years. Patiromer is not absorbed and therefore poses no risk to female partners of men who take patiromer.

This trial is categorised as Type B = somewhat higher than the risk of standard medical care.

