8.7.3 Clinical Trial

Raseline

Data gathered for the registry may be used as the baseline data for the randomised trial providing the dates are the same. If the dates differ, tests as shown in the schedule of assessments should be repeated. In addition, the following tests and measurements are mandatory prior to randomisation:

- 1. Blood collection for biomarkers
- 2. EQ5D and KCCQ questionnaires
- 3. Walk Tests
- **4.** Electronic transmission of the ECG: record and transmit 12-lead ECG to the Glasgow electrocardiology core laboratory. ECGs will be identified only by participant registration number.

Follow-up

Assessments will be repeated as at baseline on Days 7 and 60 and at 6, 12 and 24 months.

For safety visits (in addition to those above), vital signs consist only of measurements of heart rate, blood pressure and oedema grade and for biochemistry only includes sodium, potassium, urea and creatinine.

A Patient Global Assessment (PGA) which assesses the change compared to baseline will also be done at each follow-up visit as an assessment of symptoms.

Trial assessments

There will be two types of clinical assessments in this trial

a) Assessments for Efficacy at 7 and 60 days and at 6, 12 and 24 months

b) Assessments for Safety at 1, 3, 5, 14, 30days and at 3, 9, 15, 18, 21, 27 months and every 3 months thereafter until the end of the trial.

Visits for assessment of efficacy require all baseline assessments to be repeated with the exception of demography and prior medical history. Echocardiography is optional.

Visits for assessment of safety require evaluation only of symptoms, weight, concomitant cardiovascular therapy, severity of oedema, blood pressure and a blood test for measurement of serum sodium, potassium, urea and creatinine.

Longer-term efficacy and safety during the randomised trial will be assessed by reports of adverse reactions, serious adverse events and the primary composite endpoint and its components.

Participants should be encouraged at each visit to bring any remaining trial medicines (patiromer/spironolactone or eplerenone). An assessment of compliance will be made at each trial visit by research staff and documented in the eCRF. Unused IMP should be returned to the site pharmacy where it will be logged and disposed of safely.

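### Section 8.1.2 gives the additional safety visits the task of assessing magnesium, but the panel defined for them omits it: 9 of 14 post-randomisation visits to month 24, and every TX and EOS visit, have no scheduled test

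*Protocol*

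**What the plan says.** Protocol section 8.1.2 first lists the key efficacy visits: Days 7 and 60 and months 6, 12 and 24. It then describes the rest: "Additional visits are required to assess symptoms and safety (serum potassium/magnesium, renal function, blood pressure".

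The panel for those other visits is set out four times:

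- The footnotes to the schedule tables in sections 8.1.1 and 8.1.2 both read "Local Biochemistry = Sodium, Potassium, Urea, Creatinine". Magnesium appears only in the Biochem+ definition beside it.
- Section 8.7.3, under follow-up, says of safety visits that the panel "for biochemistry only includes sodium, potassium, urea and creatinine".
- Section 8.7.3, under trial assessments, asks at safety visits for a "blood test for measurement of serum sodium, potassium, urea and creatinine".

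After month 24 the only visits are the TX visits and the end-of-study visit: "TX = repeat visits every 3 months for dispensing and titration". Both are marked for the safety panel only.

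Other sections rely on magnesium results:

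- Section 3 says "Patients will be closely monitored in this trial, with regular measurements of potassium, magnesium, renal function and blood pressure". It also says that low magnesium may occur on patiromer when the MRA dose is insufficient and that, where hypotension or renal dysfunction prevents an MRA increase, "this may be corrected by magnesium supplements or by reducing the dose of patiromer".
- Section 7.2 calls for supplements below 0.75 mmol/L.
- Section 4.8 includes the percentage of patients with hypomagnesaemia at scheduled follow-up.
- Section 10.3 names changes in potassium and/or magnesium as the main concern when the drugs are combined.

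**The concern.** The additional visits in section 8.1.2 can only be the non-efficacy visits, because the efficacy visits have just been listed. Magnesium is therefore a stated purpose of visits whose blood panel does not contain it. A site that follows the panel as written will not do the monitoring that section 8.1.2 describes.

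The stake is patient safety. Supplementing and lowering the patiromer dose both need a magnesium result. The exposed patient is the one section 3 describes: on patiromer, with an MRA dose that cannot be raised. After month 24 that patient can go on receiving patiromer at TX visits with no scheduled magnesium test.

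**Working it through.** The plan states no count of magnesium tests, so there is no figure to reproduce. The check is a count from the schedule tables, with panel contents from their footnotes and section 8.7.3.

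**Visits after randomisation, to month 24**

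| Source | Visits | Biochem+ (magnesium) | Safety panel only |
|---|---|---|---|
| Table 8.1.1 | Days 3, 5, 7, 14, 30, 60 (6) | Days 7, 60 (2) | Days 3, 5, 14, 30 (4) |
| Table 8.1.2 | Months 3, 6, 9, 12, 15, 18, 21, 24 (8) | Months 6, 12, 24 (3) | Months 3, 9, 15, 18, 21 (5) |
| Total | 6 + 8 = 14 | 2 + 3 = 5 | 4 + 5 = 9 |

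So 5/14 = 36% of these visits have a scheduled magnesium test. Section 8.7.3 lists Day 1 among the safety visits, but table 8.1.1 gives it Biochem+. Counting it makes 6/15 = 40%.

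**Nominal gaps between tests**, taking six months as 365/2 = 182.5 days:

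- Day 7 to Day 60: 60 − 7 = 53 days
- Day 60 to month 6: 182.5 − 60, about 123 days
- Month 6 to month 12: about 183 days
- Month 12 to month 24: 365 days

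**After month 24.** TX and EOS carry the safety panel only, so no tests are scheduled. The Protocol trial summary gives treatment of up to 5 years. For a participant treated that long, the period without a scheduled test is 60 − 24 = 36 months. It holds TX visits at months 27, 30, …, 57, which is (57 − 27)/3 + 1 = 11, plus EOS. This is an upper limit for one participant, not an average.

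**Do the rechecks fill the gap?** After a change in patiromer or MRA dose, "serum electrolytes and creatinine should be re-checked both after 7-12 days and after 30-45 days". Acute illness also triggers a recheck. Electrolytes may reasonably include magnesium, since section 10.3 lists severe hypomagnesaemia as an electrolyte disturbance. But the rechecks do not name it, and they need a trigger. Take a patient on patiromer with potassium 4.1-4.9 mmol/L whose MRA dose is capped by hypotension or renal function. The section 9.7 titration table keeps patiromer constant in that range, and the cap prevents an MRA increase. With no dose change and no acute illness, there is no recheck.

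**The safety endpoint.** The hypomagnesaemia percentage in section 4.8 is defined over scheduled follow-up assessments, so after randomisation it can be filled at only the same 5 time points.

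**After the fix.** Magnesium in the safety panel at post-randomisation visits gives 5 + 9 = 14 of 14 to month 24, plus every TX and EOS visit.

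**The case against.** The best defence is that less frequent magnesium testing was intended and the slip lies in one parenthesis in section 8.1.2. There is support for this. Titration in section 9.7 runs on potassium alone. The IDMC focus in section 3, the events of special interest in section 11.5 and the risk table in Appendix 1 all leave magnesium out. Rewording that sentence would remove the contradiction. It would not supply a test after month 24, when patiromer is still dispensed, and it would sit badly with section 10.3.

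Several stronger readings are tempting but not supported:

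- A reader might infer that the schedule breaks the section 3 promise of regular measurement and the section 7.2 statement about measuring magnesium during the trial. Neither sets an interval, and Biochem+ arguably meets both up to month 24. Only the period afterwards is a problem under those sections.
- A reader might take a stable patient on the highest MRA dose as the exposed case. Section 3 ties the risk to insufficient MRA doses, so the relevant patient is one whose dose is held low.
- A reader might infer that hypomagnesaemia would go unrecorded. Section 4.8 separately captures related adverse reactions and serious adverse events, and these are not tied to scheduled visits.
- A reader might infer bias between arms. Both arms follow the same schedule, so the documents give no basis for that.
- A reader might want an average untested period or a trial-wide assay total. Either would need an assumed five-year calendar with no deaths. The trial is event-driven and the population has high mortality.

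Finally, the trial closed early. SAP section 1.6.1 reports 4 randomised participants, and the SAP section 2.6 listings name neither month 24 nor TX visits. That removes nearly all practical effect on the report, but not the inconsistency in the protocol.

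**Conclusion.** The point holds as an inconsistency within section 8 that should be corrected if the protocol is amended or reused. Section 8.1.2 assigns magnesium to visits whose panel excludes it. The size is 9 of 14 post-randomisation visits to month 24 without a scheduled test, a longest nominal gap of 365 days in that period, and no scheduled test afterwards.

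The counts rest only on the schedule tables and panel definitions. The 36-month upper limit assumes a participant treated for the full five years. The safety argument rests on the risk condition in section 3 and on doses staying stable. The number of missed episodes cannot be derived from the documents. The primary analysis is not affected, and the effect on the actual report is negligible.

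**What to change.** Add magnesium to the safety panel at all post-randomisation safety visits, including TX and EOS, in the footnotes to tables 8.1.1 and 8.1.2 and in both places in section 8.7.3. Leave the screening log unchanged: it shares the table row, but section 8.7.1 limits it to existing records. Name magnesium in the recheck instructions in sections 8.1.2 and 9.7.

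Adding it at TX and EOS alone would close the gap after month 24 but leave the nine earlier visits in conflict with section 8.1.2.

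The cost is one extra assay per safety visit on blood already drawn: 9 for a participant followed to month 24, then one at each TX and EOS visit. For a participant treated for five years that is at most 9 + 11 + 1 = 21. A protocol amendment is needed under section 14.10 and, if not already present, a magnesium field on the safety-visit eCRF. The SAP needs no separate change.
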